### 3.3 Hypotheses/Estimation

This trial is being conducted as an open-label study. There is no randomization in the study. Objectives and associated estimations of the study are stated in Protocol Section 3.

### 3.4 Analysis Endpoints

#### 3.4.1 Efficacy/Immunogenicity/Pharmacokinetics Endpoints

##### Primary

- **Objective Response Rate (ORR) – per RECIST 1.1 assessed by central imaging vendor**

Proportion of subjects in the analysis population who have complete response (CR) or partial response (PR) where responses are determined by RECIST 1.1 assessed by central imaging vendor.

##### Secondary

- **Duration of Response (DOR) – per RECIST 1.1 assessed by central imaging vendor**

For subjects who demonstrated CR or PR, DOR is defined as the time from first documented evidence of CR or PR until progressive disease (PD) assessed by central imaging using RECIST 1.1 or death due to any cause, whichever occurs first.

- **Duration of Response (DOR) – per PCWG3-modified RECIST 1.1 assessed by central imaging vendor**

For subjects who demonstrated CR or PR, DOR is defined as the time from first documented evidence of CR or PR until progressive disease (PD) assessed by central imaging where PD will be determined by radionuclide bone scan using RECIST 1.1/PCWG3 criteria and PD for all other tumors will be determined using RECIST 1.1 or death due to any cause, whichever occurs first.

- **Disease Control Rate (DCR) – per PCWG3-modified RECIST 1.1 assessed by central imaging vendor**

Proportion of subjects in the analysis population who have CR or PR or stable disease (SD) or Non-CR/Non-PD for at least 6 months, by central imaging vendor where PD in bone-only tumors will be determined by radionuclide bone scan using PCWG3 criteria and PD for all other tumors will be determined using RECIST 1.1.

- **PSA Response Rate**

Proportion of subjects in the analysis population who have PSA response defined as at least 50% ( $\geq 50\%$ ) decline from baseline measured twice at least 3 weeks apart, i.e. the number of subjects with PSA response divided by the total number of subjects with PSA measurement at baseline. Response must be confirmed by a second PSA value 3 or more weeks later.

- **Time to PSA Progression**

Time to PSA progression is defined as the time from first day of study treatment to the date of PSA progression. Subjects without PSA progression will be censored at the last PSA assessment date. For subjects who have a decline in PSA, the PSA progression date is defined as the date that an increase of 25% or more and an absolute increase of 2ng/mL or more from the nadir is documented.

For subjects who have no decline in PSA, the PSA progression date is defined as the date that an increase of 25% or more and an absolute increase of 2ng/mL or more, at least 12 weeks from the baseline is documented. If the PSA value at progression is less than the baseline, then PSA progression must be confirmed by a second value 3 or more weeks later.

- **Radiographic progression-free survival (rPFS) – per PCWG3-modified RECIST 1.1 assessed by central imaging vendor**

Progression-free-survival (rPFS) is defined as the time from first day of study treatment to the documented disease progression by central imaging vendor where PD in bone-only tumors will be determined by radionuclide bone scan using PCWG3 criteria and PD for all other tumors will be determined using RECIST 1.1 or death due to any cause, whichever occurs first.

- **Overall Survival (OS)**

Overall survival (OS) is defined as the time from first day of study treatment to the time of death.

- **Duration of PSA response (Cohorts 4 and 5 only)**

Duration of PSA response is defined as the time from PSA response, when the PSA value first declines by at least 50% of the baseline (must be confirmed by a second value), to the date of PSA progression at which there is an increase of 25% or more from the nadir PSA, provided the absolute increase from the nadir PSA is at least 2ng/mL.

- **Time to initiation of cytotoxic chemotherapy (Cohorts 4 and 5 only)**

Time to initiation of cytotoxic chemotherapy is defined as the time from first day of study treatment to the time of initiation of cytotoxic chemotherapy for prostate cancer.

- **Time to new-anticancer therapy (Cohorts 4 and 5 only)**

Time to new-anticancer therapy is defined as the time from first day of study treatment to the time of new-anticancer therapy for prostate cancer

- **Time to first skeletal-related event (Cohorts 4 and 5 only)**

Time to initiation of first skeletal-related event is defined as the time from first day of study treatment to the first skeletal-related event, which is defined as radiation therapy or surgery to bone, pathologic bone fracture, spinal cord compression, or change or antineoplastic therapy to treat bone pain.

See [Section 3.6.1](#) for censoring rules.

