4.2.3 Rationale for Endpoints

4.2.3.1 Efficacy Endpoints

The primary efficacy objective of this study is to evaluate the antitumor activity of pembrolizumab in subjects with mCRPC previously treated with chemotherapy. Objective response rate will be used as the primary endpoint, and objective response will be determined using RECIST 1.1 by the central imaging vendor in the measurement of soft tissue disease. Duration of response and PFS will be determined using radiographic progression. Radiographic progression for soft tissue lesions will be determined using RECIST 1.1 (Section 12.7). Radiographic progression for bone lesions will be determined by radionuclide bone scan using the consensus guidelines of the PCWG3 criteria [42, 43]. Time-to-progression endpoints, including DOR, DCR, and rPFS, will be measured until progressive disease (PD) to be defined as the point at which there has been tumor progression in soft tissue lesions by RECIST 1.1 guidelines and/or tumor progression in bone lesions detected by radionuclide bone scan by PCWG criteria (PCWG3-modified RECIST 1.1).

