5.2.2 Timing of Dose Administration

5.2.2.1 Pembrolizumab

The first infusion should be administered on the day of treatment allocation or as close as possible to the date on which the subject is allocated, ie, ≤7 days. Pembrolizumab should be administered on Day 1 of each 3 week cycle after all procedures/assessments have been completed as detailed on the Trial Flow Chart (Section 6). After the first cycle, trial treatment may be administered up to 3 days before or after the scheduled Day 1 of the cycle due to administrative reasons.

Details pertaining to the preparation and administration of pembrolizumab are provided in the Pharmacy Manual.

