7.1.2.6.2 Tumor Imaging During Trial

In the first year, on study imaging assessments must be performed every 9 weeks (63 days \pm 7 days) from the date of allocation for the first year (through week 54 \pm 7 days). Subjects who remain on treatment beyond the first year will have imaging performed every 12 weeks (84 days \pm 7 days). Imaging timing should follow calendar days from date of allocation and should not be adjusted for delays in cycle starts.

Response

Per RECIST 1.1, response should be confirmed by a repeat radiographic assessment not less than 4 weeks from the date response was first documented. The scan for confirmation of response may be performed \geq 4 weeks after the first indication of response or at the next scheduled scan, whichever is clinically indicated. Subjects who obtain a repeat scan do not need to undergo the next scheduled imaging if it is $<$ 4 weeks after the confirmation scan. Subjects will return to their regular imaging schedule starting with the next time point.

For any subject with known brain metastases at baseline, and who achieves a CR during trial treatment, a follow-up brain scan is required for confirmatory assessment of CR.

Progression

Radiographic progression for soft tissue lesions will be determined according to RECIST 1.1 (Section 12.7). Disease progression in soft tissue lesions should be confirmed by the site \geq 4 weeks after the first radiologic evidence of PD. Subjects who have unconfirmed disease progression and are clinically stable may continue on treatment at the discretion of the investigator until progression is confirmed by the site. Subjects who obtain a repeat scan do not need to undergo the next scheduled imaging if it is $<$ 4 weeks after the confirmation scan. Subjects will return to their regular imaging schedule starting with the next time point.

Subjects who have confirmed disease progression, as assessed by the site, will discontinue treatment.

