8.4 Analysis Endpoints

8.4.1 Efficacy/Immunogenicity/Pharmacokinetics Endpoints

Primary

- **Objective Response Rate (ORR) – per RECIST 1.1 assessed by central imaging vendor**

Proportion of subjects in the analysis population who have complete response (CR) or partial response (PR) where responses are determined by RECIST 1.1 assessed by central imaging vendor.

Secondary

- **Duration of Response (DOR) – per PCWG3-modified RECIST 1.1 assessed by central imaging vendor**

For subjects who demonstrated CR or PR, DOR is defined as the time from first documented evidence of CR or PR until progressive disease (PD) assessed by central imaging where PD will be determined by radionuclide bone scan using RECIST 1.1/PCWG3 criteria and PD for all other tumors will be determined using RECIST 1.1 or death due to any cause, whichever occurs first.

- **Duration of Response (DOR) – per RECIST 1.1 assessed by central imaging vendor**

For subjects who demonstrated CR or PR, DOR is defined as the time from first documented evidence of CR or PR until progressive disease (PD) assessed by central imaging using RECIST 1.1 or death due to any cause, whichever occurs first.

- **Disease Control Rate (DCR) – per PCWG3-modified RECIST 1.1 assessed by central imaging vendor**

Proportion of subjects in the analysis population who have CR or PR or stable disease (SD) for at least 6 months, by central imaging vendor where PD in bone-only tumors will be determined by radionuclide bone scan using PCWG3 criteria and PD for all other tumors will be determined using RECIST 1.1.

- **PSA Response Rate**

Proportion of subjects in the analysis population who have PSA response defined as at least 50% decline from baseline measured twice at least 3 weeks apart.

- **Time to PSA Progression**

Time to PSA progression is defined as the time from first day of study treatment to the date of PSA progression. Subjects without PSA progression will be censored at the last PSA assessment date. PSA progression is defined as the date that an increase of 25% or more and an absolute increase of 2 ng/mL or more from the nadir are documented. For subjects who have a decline in PSA during treatment, PSA progression must be confirmed by a second value 3 or more weeks later increased with respect to the nadir PSA.

- **Radiographic progression-free survival (rPFS) – per PCWG3-modified RECIST 1.1 assessed by central imaging vendor**

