### 3.5.3 Biomarker Discovery Population

The biomarker discovery population consists of the first 100 subjects with RECIST1.1 -measurable disease in Cohorts 1 and 2 who are clinically evaluable, which is defined as any subjects who received at least one dose of study drug and had at least 3 post-baseline scans, or discontinued due to radiographic/clinical progression or death before reaching week 27.

The biomarker discovery population will be used in this study for the evaluation of the association between biomarker score and clinical efficacy and subsequently to determine a biomarker cut-point (if applicable and necessary). The biomarker discovery population will be excluded from any subsequent validation analyses for any biomarker selected population, if applicable. These subjects will still be included in the general efficacy analyses for all cohorts combined and by each cohort irrespective of biomarker status.

More details will be provided in a separate biomarker analysis plan.

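### Does DCR's six-month rule need a start date, an end date and a day count written into the definition?

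*SAP*

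**What the plan says.** The sSAP (section 3.4.1) defines DCR as "Proportion of subjects in the analysis population who have CR or PR or stable disease (SD) or Non-CR/Non-PD for at least 6 months". Protocol 8.4.1 has "Proportion of subjects in the analysis population who have CR or PR or stable disease (SD) for at least 6 months", without the non-measurable category. Neither sentence says when the six months begin or end, or how many days they contain.

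Other parts of the plan bear on the missing pieces:

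- **End.** Protocol 4.2.3.1 states: "Time-to-progression endpoints, including DOR, DCR, and rPFS, will be measured until progressive disease (PD". It then defines PD by RECIST 1.1 in soft tissue and/or by bone scan.
- **Origin of the sister endpoint.** "Progression-free-survival (rPFS) is defined as the time from first day of study treatment to the documented disease progression by central imaging vendor" (sSAP 3.4.1). DCR uses the same criteria and the same central reader.
- **Missing data.** Protocol Table 9 and sSAP Table 3 count subjects with missing DCR data as not under control.
- **Scan clock.** "Imaging timing should follow calendar days from date of allocation and should not be adjusted for delays in cycle starts" (Protocol 7.1.2.6.2). Scans are every 63 days, ±7 days, in the first year.
- **Dosing lag.** The first infusion is given on the day of allocation "or as close as possible to the date on which the subject is allocated, ie, ≤7 days" (Protocol 5.2.2.1).

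**The concern.** Disease status is seen only at scans, and the six-month mark coincides with one of them. A man stable at Week 18 whose progression is found at Week 27 is controlled for six months if the count runs to the PD date. He is not controlled if it runs to his last scan without progression. For men whose deciding scan is the Week 27 scan, a day or two of scheduling, or a few days between allocation and first dose, can also tip the classification.

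DOR and rPFS have their origins and ends written out, and each has a censoring table. DCR has neither, although it is reported for every cohort. If two programmers could reach rates that differ by about as much as the confidence interval is wide, the reported DCR would be hard to interpret.

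**Working it through.** **The plan's own figure.** Neither document gives a DCR assumption. The nearest figure is the table of exact intervals for ORR (Protocol Table 10, sSAP Table 4), which uses the method planned for DCR. All 15 rows reproduce to rounding, for example 20/200 gives 6.2% to 15.0% and 24/80 gives 20.3% to 41.3%. The same method near a rate of 34–35% gives interval widths of 13.6 points (69/200), 27.6 points (17/50) and 31.1 points (14/40).

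**Where six months falls.** 365.25/2 = 182.6 days, so day 183 is the first to qualify. The Week 27 scan is due on day 3 × 63 = 189, with a window of day 182–196 from allocation. With a lag of 0–7 days it falls on day 175–196 from first dose.

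**Share of Week 27 scans before day 183** (assumption: whole days, uniform over the 15-day window):

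- From allocation, or with no lag: only day 182 falls short, 1/15 = 0.067.
- From first dose, lag uniform on 0–7 days (assumption): a lag of L days leaves L + 1 scan days short. The sum over L = 0 to 7 is 36, and 36/(15 × 8) = 0.30.
- With six months taken as 180 days, from allocation: 0.

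**Illustrative progression** (assumption: 30% of those at risk progress at each scan, no CR or PR; this corresponds to a median of about 4.0 months):

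- No PD through Week 27: 0.7³ = 0.343.
- First PD at Week 27: 0.7² × 0.3 = 0.147.
- Last scan without PD at Week 27: 0.7³ × 0.3 = 0.103.

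**Effect of scan date when the count ends at PD.** Only men with first PD at Week 27 are affected.

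- No lag: 0.147 × 0.067 = 1.0 point. DCR = 0.343 + 0.147 × 0.933 = 48.0%.
- Uniform lag: 0.147 × 0.30 = 4.4 points. DCR = 0.343 + 0.147 × 0.70 = 44.6%.
- Every subject dosed a full 7 days late (extreme case): 0.147 × 8/15 = 7.8 points.

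With exponential progression and medians of 2 to 9 months, the first two results become 0.7–1.0 and 3.2–4.4 points. Moving the cut from 168 to 183 days, with the uniform lag, moves DCR by 3.0–4.3 points over the same medians.

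**If the last scan without PD were used as the end instead:**

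- No lag: 0.343 − 0.103 × 0.067 = 33.6%, a gap of 48.0 − 33.6 = 14.4 points.
- Uniform lag: 0.343 − 0.103 × 0.30 = 31.2%, a gap of 44.6 − 31.2 = 13.4 points.
- Every scan exactly on day 189: the gap is 14.7 points, so it comes from the choice of end and not from scan dates.
- At 20% progression per scan the gap is 12.0–12.6 points; at 45% it is 11.8–13.2 points. In simulation over medians of 2–9 months, with 0–30% of events being deaths, it is 8.3–15.1 points.

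This gap is real arithmetic, but a programmer reaches it only by setting aside Protocol 4.2.3.1 in favour of a rule that neither document states.

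**Would a Week 27 visit rule be better?** Suppose control required no PD at or before Week 27 and an adequate scan without PD mapped to that visit or later.

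- A man dosed on the day of allocation with PD on day 189 has an rPFS of 189/30.44 = 6.2 months, yet would be called not controlled.
- Mapping to the nearest visit splits Weeks 18 and 27 at (126 + 189)/2 = 157.5. A stable scan on day 158, or 158/30.44 = 5.2 months, would then count as six months of control. The nearest-visit windows for patient-reported outcomes in sSAP Table 6 give the same lower limit.

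**The case for a change.** The strongest case for a change is that Protocol 4.2.3.1 is rationale text. It groups a proportion with time-to-progression endpoints, and neither the definitions nor the analysis tables repeat it. Under a PD end, a man whose last scan without progression was near day 126 is credited with six months of control. ORR is not estimated in Cohorts 3 and 5, so DCR is their only secondary response rate based on imaging. It is also an outcome in the biomarker regressions. The plan already uses Week 27 as a landmark for evaluability: "had at least 3 post-baseline scans, or discontinued due to radiographic/clinical progression or death before reaching week 27". A clarifying sentence would cost almost nothing.

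Part of this stands. The origin and the day count are unstated, the origin has to be inferred from rPFS, and no DCR rule names subjects who stop scans or start new therapy without PD.

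The rest is weaker. Rationale or not, that sentence is the only statement of DCR's end in either document, and nothing contradicts it. Dating progression when it is documented is also how the plan handles rPFS and DOR, so the credit between Week 18 and Week 27 is a shared convention and not a DCR anomaly. A subject who leaves imaging early without PD falls naturally under the missing-data rule. The Week 27 landmark serves biomarker evaluability in Cohorts 1 and 2 and does not define control. Kaplan-Meier rPFS is reported for the same cohort groupings, Cohorts 3 and 5 included, so progression-free status near six months is visible in any case.

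**Conclusion.** No change to the plan follows. The definition lacks detail that an analyst would fill in one sensible way: count from first dose as for rPFS, end at PD as Protocol 4.2.3.1 says, fix the number of days in the programming specification, and treat subjects without the needed scans as not controlled.

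On that reading, scan date and dosing lag move DCR by about 1 point with no lag and about 4.4 points with a uniform 0–7 day lag. Both figures assume 30% progression per scan, which no document supports or rules out. A uniform lag is probably pessimistic, since the protocol asks for dosing on the day of allocation or as near to it as possible. These shifts are small beside exact interval widths of about 14 points (n = 200) to 31 points (n = 40). DCR is a secondary estimate, no hypothesis is tested, and ORR and the sample size are untouched. The alternative tied to the Week 27 visit trades one imperfection for others: it can disagree with rPFS for the same man, and it can credit 5.2 months as six.

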Radiographic progression for bone lesions will be determined as described in the consensus guidelines of the Prostate Cancer Clinical Trials Working Group 3 (PCWG3) [44]. Radiographic progression of bone lesions will be defined as the appearance of ≥ 2 new bone lesions on radionuclide bone scan. Progression in bone at the first scheduled assessment at Week 9, if unaccompanied by soft tissue progression, requires a second radionuclide bone scan ≥ 6 weeks later. Progression is confirmed to have occurred at the first scheduled assessment if the confirmation bone scan shows ≥ 2 additional new lesions. Radiographic bone progression after the 9 week assessment must be confirmed ≥ 6 weeks later, if unaccompanied by soft tissue progression. Progression is confirmed if the confirmation bone scan shows the persistence of ≥ 2 new bone lesions. Subjects who have unconfirmed disease progression and are clinically stable may continue on treatment at the discretion of the investigator until progression is confirmed by the site. Subjects who have confirmed disease progression, as assessed by the site, will discontinue treatment.

If a subject with confirmed radiographic progression is clinically stable or clinically improved, and there is no further increase in the tumor dimensions at the confirmatory scan, an exception may be considered to continue treatment upon consultation with the Sponsor. Clinically stable subjects should also have at the confirmatory scan no further increase in the target lesions, no unequivocal increase in non-target lesions and no additional new lesions develop (non-worsening PD) to continue study treatment.

Imaging should continue to be performed until documented disease progression, the start of new anti-cancer treatment, withdrawal of consent or death, whichever occurs first (Table 5).

Table 5 Imaging and Treatment after 1st Radiologic Evidence of PD

	Clinically Stable		Clinically Unstable	
	Imaging	Treatment	Imaging	Treatment
1 st radiologic evidence of PD	Repeat imaging at ≥ 4 weeks to confirm PD (soft-tissue progression) Repeat bone scan at ≥ 6 weeks to confirm PD (bone progression)	May continue study treatment at the Investigator's discretion while awaiting confirmatory scan	Repeat imaging at ≥ 4 weeks to confirm PD if possible (soft-tissue progression) Repeat bone scan at ≥ 6 weeks to confirm PD if possible (bone progression)	Discontinue treatment

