7.1.2.8 Tumor Marker Assessment (PSA)

The initial Prostate-Specific Antigen (PSA) biomarker assessment at screening must be performed within 28 days prior to the date of allocation/Cycle 1.

In the first year (through week 54), on study PSA biomarker assessments must be performed every 9 weeks (63 days ± 7 days) from the date of allocation. After one year, subjects who remain on treatment will have PSA performed every 12 weeks (84 days ± 7 days). PSA timing should follow calendar days from the date of allocation and should not be adjusted for delays in cycle starts.

In Cohorts 4 and 5, screening PSA by central results are required during the screening period as part of eligibility and should be drawn and sent to the central lab to ensure the result is available in time for allocation. PSA biomarker assessment must occur every 3 weeks (± 3 days) from the date of allocation/Cycle 1 while the subject is on trial treatment (at weeks 3 and 9) up to cycle 4 (week 12) then follow the imaging schedule as described above. PSA timing should follow calendar days from the date of allocation and should not be adjusted for delays in cycle starts.

In subjects who discontinue trial treatment without documented disease progression, every effort should be made to continue monitoring their disease status by PSA biomarker assessments using the same schedule the subject was on during treatment (e.g. every 9 weeks [63 days ± 7 days from the date of allocation] or every 12 weeks [84 days ± 7 days from the date of allocation]) until: 1) the start of new anti-cancer treatment, 2) disease progression, 3) death or 4) the end of the study, whichever occurs first.

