Endpoint/Variable (Description, Time Point)	Statistical Method	Analysis Population	Missing Data Approach
ORR per RECIST 1.1 assessed by central imaging vendor	Exact method based on binomial distribution (Clopper-Pearson method)	Subjects with measurable disease at baseline in ASaT in all below populations 
 
• Cohorts 1 and 2
 
• Cohort 1
 
• Cohort 2
 
• Cohort 4
 
	Subjects with missing data are considered non-responders

DOR per RECSIT 1.1 and per PCWG3-modified RECIST 1.1 assessed by central imaging vendor	Summary statistics using Kaplan-Meier method	Responders with measurable disease at baseline in ASaT in all below populations 
 
• Cohorts 1 and 2
 
• Cohort 1
 
• Cohort 2
 
• Cohort 4
 
	Details are provided in a separate table
DCR per PCWG3-modified RECIST 1.1 assessed by central imaging vendor	Exact method based on binomial distribution (Clopper-Pearson method)	ASaT 
 
• Cohorts 1+2+3
 
• Cohorts 1+2
 
• Cohorts 4+5
 
• Each Cohort
 
	Subjects with missing data are considered disease not under control
PSA Response Rate §	Exact method based on binomial distribution (Clopper-Pearson method)	ASaT 
 
• Cohorts 1+2+3
 
• Cohorts 1+2
 
• Cohorts 4+5
 
• Each Cohort
 
	Subjects with missing data are considered non-responders
Time to PSA Progression §	Summary statistic using Kaplan-Meier method	ASaT 
 
• Cohorts 1+2+3
 
• Cohorts 1+2
 
• Cohorts 4+5
 
• Each Cohort
 
	Censored at last assessment date
Radiographic PFS per PCWG3-modified RECIST 1.1 assessed by central imaging vendor	Summary statistics using Kaplan-Meier method	ASaT 
 
• Cohorts 1+2+3
 
• Cohorts 1+2
 
• Cohorts 4+5
 
• Each Cohort
 
	Censored at last assessment date
OS	Summary statistics using Kaplan-Meier method	ASaT 
 
• Cohorts 1+2+3
 
• Cohorts 1+2
 
• Cohorts 4+5
 
• Each Cohort
 
	Censored at last date known alive

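### Time to PSA progression is censored when PSA sampling ends for progression, new therapy or death, so the Kaplan-Meier censoring is probably informative and needs companion analyses

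*SAP*

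**What the plan says.** The sSAP (section 3.4.1, Time to PSA Progression) states that "Subjects without PSA progression will be censored at the last PSA assessment date". Table 3 in sSAP 3.6.1 gives the method as "Summary statistic using Kaplan-Meier method" and the missing-data approach as "Censored at last assessment date". Protocol 8.4.1 and Table 9 agree. The reason sampling stopped plays no part in the rule.

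When sampling stops is set elsewhere:

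- **On treatment.** PSA is drawn at the imaging visits, every 9 weeks through Week 54 and then every 12 weeks, and once at discontinuation (Protocol 6.1, footnote s). Cohorts 4 and 5 have additional early readings.
- **At progression.** "Subjects who have confirmed disease progression, as assessed by the site, will discontinue treatment" (Protocol 7.1.2.6.2). Before that point, "Subjects who have unconfirmed disease progression and are clinically stable may continue on treatment at the discretion of the investigator" until the site confirms it. After confirmed progression, "an exception may be considered to continue treatment upon consultation with the Sponsor".
- **Off treatment without progression.** Protocol 7.1.2.8 asks that "every effort should be made to continue monitoring their disease status by PSA biomarker assessments", but only "until: 1) the start of new anti-cancer treatment, 2) disease progression, 3) death or 4) the end of the study, whichever occurs first".
- **After confirmed progression or new therapy.** Contact is by telephone, for survival (Protocol 7.1.5.3.1). No PSA is scheduled.

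DOR and rPFS have full censoring tables in sSAP 3.6.1, and duration of PSA response has a new-therapy rule. Time to PSA progression has only the single line, with no sensitivity analysis.

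**The concern.** Kaplan-Meier assumes that a subject censored at a given time has the same future risk as those still followed. Here most censoring before the data cut-off will come from radiographic progression, new therapy or death. These are expressions of the same disease, so the assumption is doubtful.

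Two event rules sharpen this. Under the sSAP, a subject whose PSA never fell can have an event only from 12 weeks after baseline, while the first imaging is at Week 9. A clinically unstable subject stops at first radiographic progression (Protocol Table 5 and 7.1.2.6.5), so one who stops at Week 9 with a steeply rising PSA is censored. Also, a rise from nadir that is still below baseline needs a second value at least 3 weeks later (Protocol 8.4.1 asks for confirmation after any decline). After stopping for progression no later PSA is scheduled, so that rise may never be confirmed.

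The trial is uncontrolled and estimates only, so no comparator absorbs the error. A reader may also take one minus the curve as the share of subjects who had PSA progression, which it is not.

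**Working it through.** The documents give no median, event count or precision for this endpoint, so there is no figure to reproduce. Size and direction were examined by simulation, 200,000 subjects per scenario.

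**Inputs from the documents:** the visit grid (9-weekly to Week 54, then 12-weekly), the 12-week rule (applied to everyone), and the end of sampling at progression.

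**Assumed inputs:** exponential time to PSA progression, median 18 or 27 weeks; exponential time to radiographic progression, median 12 or 18 weeks; Gaussian-copula correlation 0 to 0.7; no deaths or new therapy.

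**Benchmark.** With complete PSA follow-up, the Week 27 progression-free share is 2^(-27/27) = 0.50 for a 27-week median and 2^(-27/18) = 0.35 for an 18-week median.

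**Step 1: Kaplan-Meier against the benchmark.** Week 27 values, PSA median 27 weeks (benchmark 0.50):

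| Radiographic median (wk) | Correlation | KM, last PSA at progression visit | KM, discontinuation PSA 6 wk later | Free of PSA and radiographic progression |
|---|---|---|---|---|
| 12 | 0 | 0.50 | 0.41 | 0.11 |
| 12 | 0.3 | 0.59 | 0.46 | 0.14 |
| 12 | 0.5 | 0.66 | 0.50 | 0.16 |
| 12 | 0.7 | 0.74 | 0.53 | 0.19 |
| 18 | 0 | 0.50 | 0.44 | 0.18 |
| 18 | 0.3 | 0.57 | 0.47 | 0.22 |
| 18 | 0.5 | 0.62 | 0.50 | 0.25 |
| 18 | 0.7 | 0.68 | 0.52 | 0.29 |

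- Last PSA at the progression visit: the largest bias is 0.742 - 0.501 = +24 points. Including the 18-week PSA median, the range at correlation 0.3-0.7 is about +6 to +24.
- Discontinuation PSA six weeks later: 0.464 - 0.500 = -4 points to 0.533 - 0.501 = +3 points at correlation 0.3-0.7.
- At zero correlation the first setting has no bias. The second is biased downward (0.411 - 0.501 = -9 points; 0.436 - 0.500 = -6 points). The extra reading is taken only in subjects with progression, at weeks such as 9 + 6 = 15 or 18 + 6 = 24, and so records events before others are tested.

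**Step 2: the 12-week and confirmation rules.** Suppose further that 30% are clinically unstable and stop at first progression, and 30% need a confirming value. With the discontinuation PSA kept for the rest, the Week 27 bias becomes about +3 to +13 points at correlation 0.3-0.7, and -2 to -4 at zero.

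**Step 3: one minus Kaplan-Meier against observed incidence.** With d events among n at risk at each event time:

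- 1 - KM = sum of S(t-) × d/n, where S is the Kaplan-Meier curve for PSA progression alone.
- Cumulative incidence = sum of G(t-) × d/n, where G is the share free of PSA progression and of every competing event.

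G never exceeds S, so the incidence never exceeds 1 - KM, and it is lower once any competing event precedes a PSA event. At Week 27, over correlations 0-0.7, the gap is about 4-18 points with the discontinuation PSA and reaches about 30 points without it.

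**The case against.** A reader might infer that sampling simply stops at radiographic progression, that the Kaplan-Meier estimate is therefore known to be too favourable, and that a competing-risk estimator would correct it. The documents support none of these.

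- Clinically stable subjects may stay on treatment until progression is confirmed, at least 4 weeks later in soft tissue or 6 weeks in bone. Some may continue beyond that, and a PSA is due at discontinuation. With that reading in place the Week 27 bias can take either sign.
- Upward bias needs a positive association between PSA and radiographic progression. That is plausible but not quantified, and inclusion criterion 8 itself recognises radiographic progression without PSA progression.
- An Aalen-Johansen incidence lowers the reported share with PSA progression. In a simpler example (medians 4 and 3 months, correlation 0.6, 9-weekly visits, last PSA at the progression visit, no 12-week rule), Week 27 Kaplan-Meier is 41.7%, so 1 - KM = 58.3%, while the incidence is 48.7%, a gap of 9.6 points. Its complement, 51.3%, is further than Kaplan-Meier from the full-follow-up value of 33.8%. It answers another question and does not undo dependent censoring.

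It is also fair that this is one secondary endpoint without a hypothesis test, that rPFS and OS are reported for the same cohorts, and that the 9-week grid does not represent the early 3-weekly PSA in Cohorts 4 and 5 (about 120 of 370 subjects).

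All of this stands against a claim of known direction. It leaves intact that censoring follows the disease course, that the plan does nothing about it, and that one minus the curve is not the observed share.

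**Conclusion.** The point holds as a probable weakness of uncertain sign. Upward bias is likely if PSA and radiographic progression are strongly associated, or if many subjects stop before the 12-week or 3-week conditions can be met. Under the assumed inputs at correlation 0.3-0.7, the Week 27 bias is about -4 to +3 points with a discontinuation PSA six weeks after progression, and about +6 to +24 without it. Which is nearer the truth depends on how subjects actually leave treatment.

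The firmer conclusion is that one minus Kaplan-Meier overstates the share with observed PSA progression. The direction follows from the algebra. The size, about 4-30 points, rests on the assumed medians (radiographic 12-18 weeks) and correlations 0-0.7, and shrinks if radiographic progression is slower. The primary endpoint is unaffected.

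**What to change.** Keep the Kaplan-Meier analysis. In sSAP 3.6.1 and Table 3, with matching text in Protocol Table 9, add for each cohort and pool:

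1. A sensitivity analysis of the composite of PSA progression, radiographic progression or death, as the less favourable bound on PSA control.
2. An Aalen-Johansen cumulative incidence of PSA progression, with radiographic progression, new anticancer therapy and death as competing events. Describe it as a different estimand and not as a correction of the Kaplan-Meier bias.
3. Counts of censored subjects by reason: confirmed progression, other discontinuation, new therapy, death, data cut-off.

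The cost is a few lines of text, a little programming on data already collected, and a companion figure from the composite that will look less favourable. In the table above the composite is 0.14-0.29 at Week 27 for correlations 0.3-0.7, against Kaplan-Meier values of 0.46-0.74. No visit, sample or treatment rule changes.
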